7.2.4.1.1. Hematologic Toxicity

Treatment should not begin on Day 1 of any cycle until the absolute neutrophil count (ANC) is ≥ 1500 cells/ μ L and the platelet count is $\geq 100,000$ cells/ μ L.

Olaratumab treatment on Day 8 of any cycle should be held until ANC is > 500 cells/ μ L and platelet count is $\geq 75,000$ cells/ μ L.

7.2.4.1.2. Nonhematologic Toxicity

Specific guidelines for dose adjustments in patients who experience olaratumab IRRs may be found in Section 7.5.1.1.

General guidelines for dose modification for other nonhematologic toxicities related to olaratumab are shown in Table JGDQ.3. If more than 2 toxicity-related olaratumab dose reductions are required, olaratumab will be permanently discontinued.

Table JGDQ.3. General Guidelines for Dose Modification Due to Nonhematologic Toxicities Related to Olaratumab

Reaction Grade	Required Dose Modification
Grade 1	No dose modification is required.
Grade 2	At the investigator's discretion, the patient may continue to receive olaratumab per protocol, provided that the event does not pose a serious health risk or is easily treated.
Grade 3	For a Grade 3 toxicity not adequately controlled with appropriate supportive care, the dose must be withheld until toxicity is \leq Grade 1 or has returned to pretreatment baseline; then treatment may resume at a reduced dose of 12 mg/kg for the 15-mg/kg cohort (Phase 1a) and reduced dose of 15 mg/kg for the 20-mg/kg cohort. If toxicity recurs after therapy resumes, a second dose reduction (second dose reduction of 10 mg/kg for the 15-mg/kg cohort and 12 mg/kg for the 20-mg/kg cohort) is permitted.
Grade 4	The dose must be withheld until dose toxicity is \leq Grade 1 or has returned to baseline. Permanent discontinuation should be considered for any patient experiencing Grade 4 nonhematologic toxicity assessed as related to olaratumab. However, if resumption of dosing is deemed appropriate by the investigator, treatment may resume only after consultation with the Lilly study physician, with the dose reduced to 10 mg/kg for the 15-mg/kg cohort or to 15 mg/kg for the 20-mg/kg cohort. If Grade 4 toxicity recurs after therapy resumes, all study treatment will be discontinued.

Note: for asymptomatic Grade 3/4 laboratory abnormalities that are clinically non-significant, treatable, or reversible, treatment with olaratumab may continue without dose modifications at the discretion of the investigator.

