Investigators, together with the Lilly CRP/CRS, can declare a DLT if a patient is experiencing increasing toxicity during further cycles of treatment and it becomes clear that it will not be possible to continue on treatment without exposing the patient to excessive risk.

A dose-limiting equivalent toxicity (DLET) is an AE that meets the DLT criteria as defined above and occurs in any cycle other than Cycle 1 for a patient enrolled in the Phase 1a portion of the study.

The MTD is defined as the highest tested dose that has <33% probability of causing a DLT during Cycle 1. At the time of safety assessments for each cohort, all available safety data, including DLTs and DLETs from later cycles of treatment, will be included. In addition to the DLT assessment period in Cycle 1, safety data beyond Cycle 1 available at the time of safety review will also be taken into consideration prior to determining dose escalation, whether to enroll additional patients, or whether to proceed to the Phase 1b portion of the study.

Toxicity that is clearly and directly related to the primary disease or to another etiology is excluded from the definition of DLTs.

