7.2.4. Dose Adjustments and Delays

7.2.4.1. Olaratumab

Olaratumab dose adjustments within Cycle 1 should be avoided if possible. If a dose adjustment or delay is required during Cycle 1 in the dose-escalation phase of the study, the patient will be allowed to continue but may be replaced if deemed appropriate by the Lilly CRP/CRS and investigator.

If a patient treated at a given dose level experiences a DLT (as defined in Section 7.2.2.2), then treatment will be suspended for that patient. Dosing may restart after recovery from toxicity at a lower dose after consultation between the investigator and Lilly CRP/CRS. If a toxicity does not meet the criteria for a DLT in Cycle 1 (or a DLET) but nonetheless requires omission of dose(s) for tolerability, then dosing may resume at the same dose or reduced dose after the toxicity resolves to baseline; however, the dose(s) omitted for tolerability during a cycle will not be replaced. Treatment may be delayed for up to 14 days to allow a patient sufficient time for recovery from study drug-related toxicity. If Day 8 dosing is delayed for approximately 14 days, the patient should resume treatment with Day 1 treatment for the next cycle.

The olaratumab dose for a patient should be reduced for all subsequent cycles of therapy, if the investigator determines that it is in the best interest of the patient or if the patient experienced at a DLT. For such patients requiring a dose reduction, re-escalation to the original dose level is not permitted. Patients who require more than 2 dose reductions of olaratumab will be discontinued from olaratumab treatment. If a patient experiences a DLET at a reduced dose level, then the patient will be discontinued from study treatment.

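### In the 20-mg/kg cohort, the Grade 4 row of Table JGDQ.3 states no lower olaratumab dose for a Phase 1b patient already reduced to 15 mg/kg

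*Protocol*

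**What the plan says.** Table JGDQ.3 in Protocol Section 7.2.4.1.2 governs olaratumab dosing after related nonhematologic toxicity other than infusion reactions.

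- **Grade 3, not controlled by supportive care.** Dosing is held until recovery and may then resume at a "reduced dose of 12 mg/kg for the 15-mg/kg cohort (Phase 1a) and reduced dose of 15 mg/kg for the 20-mg/kg cohort". If the toxicity returns, the table permits a "second dose reduction of 10 mg/kg for the 15-mg/kg cohort and 12 mg/kg for the 20-mg/kg cohort".
- **Grade 4.** Dosing is held until recovery, and stopping for good should be considered. If the investigator thinks resumption appropriate, it requires prior consultation with the sponsor's study physician, "with the dose reduced to 10 mg/kg for the 15-mg/kg cohort or to 15 mg/kg for the 20-mg/kg cohort". The row ends: "If Grade 4 toxicity recurs after therapy resumes, all study treatment will be discontinued".
- **Cap.** The text above the table adds: "If more than 2 toxicity-related olaratumab dose reductions are required, olaratumab will be permanently discontinued".

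Three other sections bear on the point.

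- Section 7.2.2.1 opens Phase 1b at 20 mg/kg if no more than 1 of 6 evaluable patients at that level has a DLT.
- Section 7.2.4.1 ends study treatment for a DLET at a reduced dose. For a toxicity that is neither a Cycle 1 DLT nor a DLET but leads to omitted doses, it says "then dosing may resume at the same dose or reduced dose after the toxicity resolves to baseline". After a DLT it says "Dosing may restart after recovery from toxicity at a lower dose after consultation".
- Section 7.2.2.2 defines DLTs for Cycle 1 and DLETs for Phase 1a patients only. It adds that investigators, with the sponsor's clinical staff, "can declare a DLT if a patient is experiencing increasing toxicity during further cycles of treatment".

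**The concern.** In the 20-mg/kg cohort, the Grade 4 resumption dose equals the first Grade 3 reduction dose. A patient who has already taken that Grade 3 step and then has a Grade 4 event finds, as the only dose in the row, the one at which the event occurred. The row is written as a dose reduction, yet for this patient its number gives none.

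Confirming safety and tolerability at the recommended dose is the primary objective of Phase 1b. The dose that sites take into a discussion after a Grade 4 toxicity should therefore be unambiguous. What is at stake is the handling of individual patients, not any estimate the study will report.

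**Working it through.** The plan states no figure to reproduce. The check is a table lookup followed by a search for any rule that overrides it.

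**Inputs.** The Grade 3 and Grade 4 doses come from Table JGDQ.3. Olaratumab is given on Days 1 and 8, so there are two doses per 21-day cycle (Table JGDQ.2).

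**Step 1. Size of the Grade 4 cut.** Cut = (dose at onset − stated dose) / dose at onset.

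| Cohort | Dose at onset | Stated Grade 4 dose | Cut |
|---|---|---|---|
| 20 mg/kg | 20 | 15 | (20 − 15)/20 = 25% |
| 20 mg/kg | 15, after one Grade 3 step | 15 | (15 − 15)/15 = 0% |
| 15 mg/kg | 15 | 10 | (15 − 10)/15 = 33.3% |
| 15 mg/kg | 12, after one Grade 3 step | 10 | (12 − 10)/12 = 16.7% |

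The 15-mg/kg cohort goes straight to its lowest step, so a patient with one earlier reduction still gets a real cut. The 20-mg/kg cohort goes only to its first step, so that patient gets none.

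**Step 2. Does another rule force a lower dose?** Take a Phase 1b patient on 15 mg/kg with a first Grade 4 event after Cycle 1.

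- *Cycle 1 DLT rule:* does not apply, because the event is after Cycle 1.
- *DLET stop at a reduced dose:* does not apply, because DLETs are confined to Phase 1a patients, who do not enter Phase 1b (Section 7.2.3).
- *Grade 4 recurrence stop:* does not apply, because this is the first Grade 4 event.
- *Cap of two reductions:* not reached, because one has been used.
- *General resumption sentence in Section 7.2.4.1:* allows the same or a lower dose, so it forces nothing.
- *Consultation with the sponsor's physician:* mandatory before resuming, but no dose is attached.
- *Considering discontinuation, a reduction in the patient's interest, a late-cycle DLT:* discretionary. A declared DLT would lead to a lower dose, but nobody is obliged to declare one.

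A patient already at 12 mg/kg is covered. Both reductions are used, so needing another triggers the cap.

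**Step 3. Comparison with Grade 3 in the same patient.** For a recurrent Grade 3 toxicity, 12 mg/kg is permitted, a cut of (15 − 12)/15 = 20%. Per cycle that is 2 × 12 = 24 mg/kg against 2 × 15 = 30 mg/kg under the Grade 4 row, and 30/24 = 1.25. For a new, different Grade 3 toxicity, the first step read literally also gives 15, so there is no difference. If the Grade 4 event is the earlier toxicity returning at a higher grade, both rows can be read to apply, one giving 12 and the other 15.

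**Step 4. With the dose keyed to onset.** 15 to 12 is (15 − 12)/15 = 20%.

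**The case against.** The best defence is that the row plainly intends a cut. It sits under a heading of required modifications and speaks of a reduced dose, so 15 mg/kg was surely written with a patient on 20 in mind. On that reading this is an unaddressed corner of a table of general guidelines, and the specific Grade 4 row should prevail over the general sentence that allows the same dose. Resumption also needs the sponsor's physician, who would know the current dose. That is fair as to intent, and it rules out reading the protocol as ordering these patients to continue unchanged. It does not supply the missing number: 12 mg/kg appears only in the Grade 3 recurrence step.

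The situation is also a long conjunction, and this stands. Phase 1b must run at 20 mg/kg. A related Grade 3 reduction must come first, then a first related Grade 4 event after Cycle 1. The event must not be an infusion reaction, because Grade 3 or 4 reactions end olaratumab (Table JGDQ.5). It must not be a laboratory abnormality covered by the table's note. Recovery must fit the 14-day delay limit in Section 7.2.4.1, although a Study Schedule footnote on visit windows allows longer delays in later cycles by agreement with the sponsor. Discontinuation must have been considered and rejected.

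A reader might infer that the plan generally gives a higher dose after a worse toxicity, by 25%. The documents do not support that. The contrast holds only against a recurrent Grade 3 toxicity, where 12 mg/kg is permitted rather than required.

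**Conclusion.** The point holds as a minor safety wording correction. In the situation described, the only stated resumption dose is the dose at which the Grade 4 event occurred (0% cut), and no mandatory Phase 1b rule sets a lower one.

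This assumes that Phase 1b runs at 20 mg/kg and that Table JGDQ.3 applies there. The Grade 3 row supports the second assumption: it labels only the 15-mg/kg cohort as Phase 1a. If Phase 1b runs at 15 mg/kg, the Grade 4 row gives a real cut (16.7% from 12 mg/kg).

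The documents give no rate of olaratumab-related Grade 4 events, so the number affected among the roughly 25 planned Phase 1b patients cannot be estimated. It would be wrong to conclude that Phase 1b patients are left without protection or that the safety results are compromised. The mandatory consultation and the discretionary safeguards would often prevent an unchanged dose, and no endpoint or analysis depends on this clause.

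**What to change.** Change only the dose clause in the Grade 4 row, for example to:

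> The resumed dose is 10 mg/kg in the 15-mg/kg cohort. In the 20-mg/kg cohort it is 15 mg/kg if the event arose at 20 mg/kg and 12 mg/kg if it arose at 15 mg/kg. The resumed dose must always be lower than the dose in use at onset; if there is no lower step, olaratumab is permanently discontinued.

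Keep the mandatory consultation, the Grade 4 recurrence stop, the Phase 1a DLET stop and the cap of two reductions.

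The Grade 3 row need not change. If the sponsor also wants it keyed to the current dose, the revision must keep the limitation to toxicity not adequately controlled by supportive care and the permissive wording on resumption. Otherwise it could force reductions for controlled events, or stop olaratumab before two reductions have been used.

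The cost is one clause in the table and a clarification to sites. Sample size, visits and analyses are unchanged.

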7.2.4.2. Pembrolizumab

Adverse events (both nonserious and serious) associated with pembrolizumab exposure may represent an immunologic etiology. These immune-related AEs (irAEs) may occur shortly after the first dose or several months after the last dose of treatment and may affect more than one body system simultaneously. Therefore, early recognition and initiation of treatment is critical to reduce complications. Based on existing clinical study data, most irAEs were reversible and could be managed with interruptions of pembrolizumab, administration of corticosteroids and/or other supportive care. For suspected irAEs, ensure adequate evaluation to confirm etiology or exclude other causes. Additional procedures or tests such as bronchoscopy, endoscopy, and/or skin biopsy may be included as part of the evaluation. Based on the severity of irAEs, withhold or permanently discontinue pembrolizumab and administer corticosteroids. Dose modification and toxicity management guidelines for irAEs associated with pembrolizumab are provided in [Table JGDQ.4](#). See [Section 7.5.2](#) for supportive care guidelines for pembrolizumab, including use of corticosteroids.

Table JGDQ.4. Dose Modification and Toxicity Management Guidelines for Immune-Related AEs Associated with Pembrolizumab

General instructions:
 
Corticosteroid taper should be initiated upon AE improving to Grade 1 or less and continue to taper over at least 4 weeks.
 
For situations where pembrolizumab has been withheld, pembrolizumab can be resumed after AE has been reduced to Grade 1 or 0 and corticosteroid has been tapered. Pembrolizumab should be permanently discontinued if AE does not resolve within 12 weeks of last dose or corticosteroids cannot be reduced to ≤ 10 mg prednisone or equivalent per day within 12 weeks.
 
For severe and life-threatening irAEs, IV corticosteroid should be initiated first followed by oral steroid. Other immunosuppressive treatment should be initiated if irAEs cannot be controlled by corticosteroids.
				
Immune-related AEs	Toxicity grade or conditions (CTCAEv4.0)	Action taken to pembrolizumab	irAE management with corticosteroid and/or other therapies	Monitor and follow-up
Pneumonitis	Grade 2	Withhold	Administer corticosteroids (initial dose of 1-2 mg/kg prednisone or equivalent) followed by taper	
Monitor participants for signs and symptoms of pneumonitis
 
Evaluate participants with suspected pneumonitis with radiographic imaging and initiate corticosteroid treatment
 
Add prophylactic antibiotics for opportunistic infections

	Grade 3 or 4, or recurrent Grade 2	Permanently discontinue		
Diarrhea / Colitis	Grade 2 or 3	Withhold	Administer corticosteroids (initial dose of 1-2 mg/kg prednisone or equivalent) followed by taper	
Monitor participants for signs and symptoms of enterocolitis (ie, diarrhea, abdominal pain, blood or mucus in stool with or without fever) and of bowel perforation (ie, peritoneal signs and ileus). Participants with \geq Grade 2 diarrhea suspecting colitis should consider GI consultation and performing endoscopy to rule out colitis.
 
Participants with diarrhea/colitis should be advised to drink liberal quantities of clear fluids. If sufficient oral fluid intake is not feasible, fluid and electrolytes should be substituted via IV infusion.

	Grade 4	Permanently discontinue		
AST / ALT elevation or Increased	Grade 2	Withhold	Administer corticosteroids (initial dose of 0.5- 1 mg/kg prednisone or equivalent) followed by taper	Monitor with liver function tests (consider weekly or more frequently until liver enzyme value returned to baseline or is stable)

bilirubin	Grade 3 or 4	Permanently discontinue	Administer corticosteroids (initial dose of 1-2 mg/kg prednisone or equivalent) followed by taper	
Type 1 diabetes mellitus (T1DM) or Hyperglycemia	Newly onset T1DM or Grade 3 or 4 hyperglycemia associated with evidence of β -cell failure	Withhold	Initiate insulin replacement therapy for participants with T1DM Administer anti-hyperglycemic in participants with hyperglycemia	Monitor participants for hyperglycemia or other signs and symptoms of diabetes.
Hypophysitis	Grade 2	Withhold	Administer corticosteroids and initiate hormonal replacements as clinically indicated.	Monitor for signs and symptoms of hypophysitis (including hypopituitarism and adrenal insufficiency)
	Grade 3 or 4	Withhold or permanently discontinue ¹		
Hyperthyroidism	Grade 2	Continue	Treat with non-selective beta-blockers (e.g., propranolol) or thionamides as appropriate	Monitor for signs and symptoms of thyroid disorders.
	Grade 3 or 4	Withhold or permanently discontinue ¹		
Hypothyroidism	Grade 2-4	Continue	Initiate thyroid replacement hormones (eg, levothyroxine or liothyronine) per standard of care	Monitor for signs and symptoms of thyroid disorders.
Nephritis and Renal dysfunction	Grade 2	Withhold	Administer corticosteroids (prednisone 1-2 mg/kg or equivalent) followed by taper.	Monitor changes of renal function
	Grade 3 or 4	Permanently discontinue		
Myocarditis	Grade 1 or 2	Withhold	Based on severity of AE administer corticosteroids	Ensure adequate evaluation to confirm etiology and/or exclude other causes
	Grade 3 or 4	Permanently discontinue		
All other immune-related AEs	Intolerable/ persistent Grade 2	Withhold	Based on type and severity of AE administer corticosteroids	Ensure adequate evaluation to confirm etiology and/or exclude other causes
	Grade 3	Withhold or discontinue based on the type of AE		

		event. Events that require discontinuation include and not limited to: Guillain-Barre Syndrome, encephalitis		
	Grade 4 or recurrent Grade 3	Permanently discontinue		

¹ Withhold or permanently discontinue pembrolizumab is at the discretion of the investigator or treating physician.

NOTE:

For participants with Grade 3 or 4 immune-related endocrinopathy where withhold of pembrolizumab is required, pembrolizumab may be resumed when AE resolves to \leq Grade 2 and is controlled with hormonal replacement therapy or achieved metabolic control (in case of T1DM).

Abbreviations: AE = adverse event; ALT = alanine aminotransferase; AST = aspartate aminotransferase; CTCAE = Common Terminology Criteria for Adverse Events; GI = gastrointestinal; irAE = immune-related adverse event; IV = intravenous; T1DM = Type 1 diabetes mellitus.

Note: Patients who have asymptomatic or clinically non-significant Grade 3 or 4 lipase or amylase elevations (that is, not associated with clinical symptoms or radiological signs of pancreatitis) which are transient as demonstrated by a decrease of at least 1 CTCAE Grade within 7 days ± 3 days of onset will not require pembrolizumab discontinuation or modification. If the elevation has not decreased at least 1 CTCAE Grade within this time window, pembrolizumab treatment may only continue after consultation and discussion with the Sponsor.

7.3. Method of Assignment to Treatment

Before a patient's enrollment into the study, an eligibility check must be conducted between the investigational site and Lilly clinical research personnel to confirm that the patient meets all eligibility criteria. Upon confirmation of eligibility, the sponsor will confirm the dose and identification number assignment for the patient. No dose escalations (that is, to the next cohort) can occur without prior discussion and agreement with the responsible Lilly CRP/CRS.

If investigators have eligible patients who have consented concurrently, more than 3 patients may be entered at a particular dose level provided that accrual has not ceased due to excessive toxicity. This enrollment procedure is allowed because of the advanced disease state of this patient population and the screening involved in defining eligibility. This event should be approved by the sponsor following discussions with the investigators.

7.4. Blinding

This is an open-label study.

7.5. Concomitant Therapy

No other chemotherapy, radiotherapy, immunotherapy, cancer-related hormone therapy, or experimental drugs will be permitted while the patients are on this study. The need for any form of radiotherapy will be cause for early discontinuation from study treatment (palliative radiotherapy is permitted if clinically indicated, after discussion with the Lilly CRP/CRS). In addition, any disease progression requiring other forms of specific antitumor therapy will also necessitate discontinuation from study treatment. Appropriate documentation for all forms of premedications, supportive care, and concomitant medications must be captured on the eCRF. Replacement hormonal therapy initiated before study entry will be allowed.

Patients should receive full supportive care with the exception that the routine use of G-CSF is not permitted during this study. Patients should not receive G-CSF prophylactically in any cycle. G-CSFs may only be used for patients who have ANC<0.5 × 10⁹, neutropenic fever, or documented infections while neutropenic. G-CSFs must be discontinued at least 24 hours before the start of the next cycle of treatment. Should the use of hematopoietic colony-stimulating factors (CSFs) be necessary, follow the American Society of Clinical Oncology (ASCO) recommendations for the use of CSFs (Smith et al. 2006). If clinically indicated at any time during the study, erythropoietin and packed red blood cell transfusions may be used according to ASCO guidelines (Rizzo et al. 2008).

All concomitant medications should be recorded throughout the patient's participation in the study.

7.5.1. *Supportive Care Guidelines for Olaratumab*

